#### Outcomes

##### *Primary Outcome*

- Change from baseline in NRS pain scale at week 4 (Appendix B).

##### *Secondary Outcomes*

- Change from baseline in NRS pain scale at days 2, 6, and 14.
- Difference in change from baseline in NRS pain scale at days 2, 6, 14, and 28 between ILTAC-10, ILTAC-20, ILTAC-40.
- Change from baseline in HS-PGA score at week 2 and 4.
- Difference in change from baseline in HS-PGA score at week 2 and 4 between ILTAC-10, ILTAC-20, ILTAC-40.
- Change from baseline in objective markers of inflammation (c-reactive protein [CRP], erythrocyte sedimentation rate [ESR], and interleukin-6 [IL-6]) at week 2 and 4.

- Change from baseline in subjective markers of inflammation (erythema, edema, and suppuration) at week 2 and 4.
- Change from baseline in lesion size at week 2 and 4.
- Difference in change from baseline in lesion size at week 2 and 4 between ILTAC-10, ILTAC-20, ILTAC-40.
- Change from baseline in Patient-Reported Outcomes Measurement Information System (PROMIS) measure of physical functioning at days 2, 6, 14, and 28.
- Difference in change from baseline in PROMIS at days 2, 6, 14, and 28 between ILTAC-10, ILTAC-20, ILTAC-40.
- Proportion of subjects reporting side effects at days 2, 6, 14, and 28.
- Difference in proportion of subjects reporting side effects at days 2, 6, 14, and 28 between ILTAC-10, ILTAC-20, ILTAC-40.
- Baseline patient satisfaction.
- Change from baseline in patient satisfaction at days 2, 6, 14, and 28.
- Serum cortisol and ACTH levels at week 2 and 4.
- Change in serum cortisol and ACTH levels from week 2 to 4.

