#### Intralesional Triamcinolone Treatment Administration

While HS patients may have multiple sites of symptomatic disease, participants on this protocol will only receive treatment in up to three anatomic regions. These will generally be the most bothersome lesions to the patient. Networks of sinus tracks or the confluence of multiple nodules will be excluded as target treatment sites.

Treatment will only be administered by the blinded clinician on this study. Additionally, the clinical assessor and the patient will be blinded to the treatment group assigned. The patient will either receive normal saline, ILTAC-10, ILTAC-20, or ILTAC-40. Each lesion will be injected with up to 2 mL in up to 3 anatomic areas. The maximum treatment volume is 3 mL.

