#### c) Outcome Measures Pertaining to Each Aim

- *Aim 1:* To compare efficacy of ILTAC-10, ILTAC-20, and ILTAC-40 versus placebo, we will measure the change from baseline in pain, objective and subjective markers of inflammation, physical functioning, and lesion size as well as comparing these changes among the different treatment groups. Change from pain baseline will be quantified by comparison of the NRS pain scale across different treatment groups (Appendix B). Objective markers of inflammation include c-reactive protein (CRP), erythrocyte sedimentation rate (ESR), and interleukin-6 (IL-6), which will be obtained from chart review of standard of care initial, 2 week, and 4 week follow-up HS visit. Erythema and edema will be measured clinically based on a 5-point ordinal scale (Appendix E). Suppuration will be measured on a dichotomous scale, by the presence or absence of purulent drainage from the lesion. Physical functioning will be measured by change from baseline in the Patient-Reported Outcomes Measurement Information System (PROMIS) measure of physical functioning. Separate forms will be administered for adult and pediatric participants. A one point change, either positive (improvement) or negative (decline), will be considered clinically meaningful (Appendix F and Appendix G). Lesion size will be measured in centimeters at baseline and during the week 2 and 4 visit.

- *Aim 2:* Side effects of ILTAC-10, ILTAC-20, and ILTAC-40 that will be investigated include thinning/atrophy of the skin, acneiform lesions, capillary dilations, and dyschromia. Hypothalamic-pituitary-adrenal (HPA) axis suppression will be obtained through chart review of standard of care serum 8 AM cortisol and ACTH levels at week 2 and 4 follow-up HS visits. Self-evaluations will be conducted by the patient and documented via telephone interviews. Clinical-evaluations will be conducted at the follow-up visits.
- *Aim 3:* To measure the patient's satisfaction after treatment, we will compare the results from the satisfaction survey between the different treatment groups at baseline, day 2, day 6, week 2, and week 4. The patient satisfaction survey will address disease control, and response to injection (in terms of pain, drainage, and lesion size), and quality of life (Appendix D).

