## 7.0 DATA ANALYSIS

- a) Statistical Methods  
We will analyze the data from the study using an intention to treat approach. Categorical variables, including presence of side effects, drainage, and physical function, will be analyzed with chi square tests. Continuous variables, such as NRS pain scale, markers of inflammation, and lesion size, will be analyzed by T-test. Sensitivity analyses or exploratory analyses may be performed to examine the effect difference for race or gender. In the unlikely case patients do not receive the treatment they will still be randomized for analysis using a per protocol approach. All statistical tests will be 2-sided, with  $p < 0.05$  considered significant.
- b) There will be no interim analysis or early stopping of the study.
- c) Confounding and effect modification will be addressed by randomization of the subjects and blinding of both the investigators and the participants.
- d) If subjects are lost to follow up, they will be analyzed in the group to which they were initially randomized.

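### Lesion outcomes have no stated unit of analysis: the t-test and chi-square are named with no per-patient summary and no allowance for several lesions in one patient

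*Combined protocol and SAP*

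**What the plan says.** All places are in the combined protocol and SAP.

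- **Treatment.** Section 2.0 (Study Design, Number of Treatment Groups) randomises patients 1:1:1:1 to one of four treatments. Under Intralesional Triamcinolone Treatment Administration, "participants on this protocol will only receive treatment in up to three anatomic regions". On which lesions are chosen it adds: "These will generally be the most bothersome lesions to the patient". Injection is by lesion: "Each lesion will be injected with up to 2 mL in up to 3 anatomic areas". The volume table in section 2.0 a) is also indexed by the size of the individual lesion.
- **Outcomes.** Secondary Outcomes includes "Change from baseline in lesion size at week 2 and 4", with a separate entry comparing the three active doses. Section 2.0 c), Aim 1, says: "Lesion size will be measured in centimeters at baseline and during the week 2 and 4 visit". It also says: "Suppuration will be measured on a dichotomous scale, by the presence or absence of purulent drainage from the lesion". Erythema and edema are graded clinically on the Appendix E scales, again with no statement of which lesion is graded.
- **Analysis.** Section 7.0 a) says: "Continuous variables, such as NRS pain scale, markers of inflammation, and lesion size, will be analyzed by T-test". Drainage is listed among the categorical variables for chi-square tests. All tests are two-sided at 0.05.
- **Not stated.** There is no target lesion, no rule for combining lesions within a patient, no unit of analysis for lesion outcomes, and no method for clustered data.

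**The concern.** A patient with two or three injected lesions yields two or three sizes and two or three suppuration readings at each visit. Those readings share one host and one randomised treatment, so they are likely to be positively correlated. The two-sample t-test and the chi-square test assume independent observations. If an analyst puts one lesion on each row, the tests count more information than 30 randomised patients per arm supply: standard errors come out too small and false positives rise.

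Even if lesions are not pooled, section 7.0 cannot be applied to a patient with several lesions until someone chooses a rule. Pooled lesions, a target lesion, the mean, the sum, the largest, and any suppuration all remain open, and the choice could be made after the data are seen. Lesion size and the clinical signs of inflammation are the main local efficacy measures under Aim 1 besides pain, so the rule should be fixed beforehand.

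**Working it through.** **1. The plan's own figure.** Table 1 concerns pain, one score per patient. Inputs: difference in mean change 1, SD 1 at both times, correlation 0.1, two-sided alpha 0.05, 30 per arm.

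- SD of change = √(2 − 2 × 0.1) = 1.342.
- Noncentrality = 1 / (1.342 × √(2/30)) = 2.887, with 58 degrees of freedom and critical value 2.002.
- Power = 0.8102, as printed (0.81021). The other eight rows also reproduce.

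The sample size is therefore a per-patient calculation and stands. The documents give no corresponding figure for lesion outcomes.

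**2. Inputs for the lesion calculation.**

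- Patients per arm: 30 (section 3.0 b).
- Nominal alpha: 0.05, two-sided (section 7.0 a).
- Lesions per patient, m: **assumption**. The documents cap areas at three, not lesions. I take two, three, and a mix.
- Within-patient correlation (ICC) of the lesion outcome: **assumption**, 0.1 to 0.7.

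**3. Formulas.** With m lesions for every patient, the design effect is DE = 1 + (m − 1) × ICC. The naive standard error is too small by a factor √DE, so the actual type I error of one between-arm comparison is 2 × [1 − Φ(1.96/√DE)].

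For equal thirds with one, two and three lesions, m is replaced by Σm²/Σm = (1 + 4 + 9)/(1 + 2 + 3) = 2.333, so DE = 1 + 1.333 × ICC.

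**4. Results if each lesion is a row.**

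| ICC | Two lesions: DE, type I | Three lesions: DE, type I | Mixed 1/2/3: DE, type I |
|---|---|---|---|
| 0.1 | 1.1, 6.2% | 1.2, 7.4% | 1.133, 6.6% |
| 0.3 | 1.3, 8.6% | 1.6, 12.1% | 1.400, 9.8% |
| 0.5 | 1.5, 11.0% | 2.0, 16.6% | 1.667, 12.9% |
| 0.7 | 1.7, 13.3% | 2.4, 20.6% | 1.933, 15.9% |

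Worked cell (three lesions, ICC 0.5): DE = 1 + 2 × 0.5 = 2.0; 1.96/√2 = 1.386; 2 × [1 − Φ(1.386)] = 16.6%.

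With three lesions per patient, the 90 lesions per arm carry the information of 90/1.2 = 75 independent lesions at ICC 0.1, and 90/2.4 = 37.5 at ICC 0.7.

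**5. Simulation check, 30 patients per arm.**

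- Lesion-level t-test, ICC 0.1 to 0.7: 6.1% to 13.7% with two lesions and 7.3% to 20.9% with three (20,000 trials per setting).
- Mixed counts: 6.5%, 9.7%, 13.2%, 16.4% at ICC 0.1, 0.3, 0.5, 0.7 (10,000 trials per setting).
- Lesion-level chi-square, three lesions, assuming 40% of lesions drain: 7.6% to 21.0%.
- One mean per patient, then the same t-test (equal lesion counts): 4.7% to 5.2%.

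The last line shows that the t-test itself is sound once each patient contributes one value.

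**The case against.** The strongest reply is that the plan never says lesions will be separate rows. Its analysis language is about subjects: intention to treat, lost subjects kept in their randomised group, and a power report in terms of two groups of subjects. With one value per patient, both named tests are valid. This stands. A reader might infer that section 7.0 commits to a lesion-level analysis or names tests that are wrong in themselves; the documents support neither. What remains is that no patient-level value is defined, so the error rates above are conditional.

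Other points against, and what stands of them:

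- **Three lesions.** A reader might take the limit of three to be a count of lesions. It is a count of areas, and eligibility requires only one inflamed nodule or abscess, so single-lesion patients will dilute the inflation. The 3 mL patient total also limits how many large lesions can be treated: three of 2.5 cm would take 3 × 1.2 = 3.6 mL on the plan's volume table. It does not rule out several smaller ones: three of 2.0 cm take 3 × 1.0 = 3.0 mL.
- **The earlier trial.** A reader might infer that the protocol repeats a fault it condemns. Section 1.0 faults that trial for randomising lesions rather than participants, because systemic effects of the injection were not accounted for. That concerns one arm's drug reaching lesions in another arm, not correlated errors in the analysis. This trial answers it by giving each patient one treatment, so there is no self-contradiction.
- **Drainage.** In section 7.0 it could mean the patient-level survey item (Appendix D, item 6). The wording there refers to presence, which fits the yes/no suppuration measure better than a five-level rating, but either reading is possible. Lesion size has no such ambiguity.
- **Assumed correlation.** No ICC is given, and 20.6% needs both three lesions in every patient and an ICC of 0.7. It is the top of the range, not a central estimate.

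**Conclusion.** The point holds as a gap in specification with a conditional error. Section 7.0 leaves the unit of analysis open for outcomes recorded on lesions, and the two tests it names are valid only with one value per patient.

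If lesions are pooled as independent rows, type I error for a nominal 5% comparison is about 6-13% with two lesions per patient, 7-21% with three, and 6.5-16% with equal thirds having one, two and three. These figures rest on an assumed ICC of 0.1-0.7 and on assumed lesion counts. The direction rests on the correlation being positive, which is plausible because lesions in one patient share a host and a treatment.

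The affected outcomes are secondary: lesion size, erythema, edema and suppuration. A reader might extend the point to the primary result. That would be wrong, since NRS pain is one score per patient and Table 1 reproduces. The gap should be closed before unblinding, but it does not threaten the primary comparison.

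**What to change.** In section 7.0, state that the patient is the unit of analysis for all lesion outcomes, say which lesions count (for example, all lesions injected at visit 1), and choose one of two routes:

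- **One prespecified value per patient.** For size, use the mean change in largest diameter over the injected lesions, compared between arms with adjustment for the baseline value. For suppuration, use any suppuration yes/no. Define the erythema and edema summaries in the same way. A mean is preferable to a sum of diameters, which moves with the number of lesions.
- **A clustered model.** Use a mixed model for lesion size with patient as the cluster and baseline lesion size as covariate. Use GEE clustered on patient for suppuration, with a small-sample correction because there are only about 30 patients per arm.

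The summary or the clustering deals with the correlation; baseline adjustment is there for precision and does not replace it. Section 7.0 should also say whether drainage means suppuration as defined in section 2.0 c) or the Appendix D item.

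The cost is some SAP wording and slightly more modelling. Baseline lesion size is already collected, so no new data or visits are needed. Intervals will be wider than from pooled lesions, but valid.

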## 2.0 STUDY DESIGN

### a) Study Design

[figure not shown]
A double-blinded, randomized, placebo-controlled study examining the relative efficacy of ILTAC-10, ILTAC-20, and ILTAC-40 versus placebo for acute flares of HS in subjects with moderate to severe HS.

The duration of the study will be approximately 4 weeks for each enrolled patient and will include an initial screening/randomization/treatment visit and a 4-week follow-up period.

During the initial visit, subjects who meet the study's eligibility criteria will be randomized to receive either ILTAC-10, ILTAC-20, ILTAC-40, or normal saline (NS) placebo in a 1:1:1:1 ratio. The volume of ILTAC or NS administered is calculated based on the largest dimension of the HS lesion, which is measured by its greatest width in mm. For example, if a lesion is irregular in shape, measuring 22mm by 18mm, 22mm will be the largest dimension used for calculating volume. The administered volume (ml) is scaled by increments of 0.2ml, which corresponds to the HS lesion size, and ranges from 0.2ml to 2.0ml. The maximum volume of either ILTAC-10, ILTAC-20, ILTAC-40 or NS administered to any given HS lesion is 2.0ml.

**Figure 1.** Hidradenitis Suppurativa Lesion Size and Volume of administration of ILTAC-10, ILTAC-20, ILTAC-40, or normal saline placebo.

| HS lesion size (cm) | Volume (ml) |
|---------------------|-------------|
| 0.0 – 0.49          | 0.2         |
| 0.5 – 0.99          | 0.4         |
| 1.0 – 1.49          | 0.6         |
| 1.5 – 1.99          | 0.8         |
| 2.0 – 2.49          | 1.0         |
| 2.5 – 2.99          | 1.2         |
| 3.0 – 3.49          | 1.4         |
| 3.5 – 3.99          | 1.6         |
| 4.0 – 4.49          | 1.8         |
| 4.5 – 5.0           | 2.0         |

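### Change in lesion size is to be compared by t-test without using baseline size: the test is valid, but it can lose precision on this secondary endpoint

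*Combined protocol and SAP*

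**What the plan says.** Section 2.0, Secondary Outcomes, lists "Change from baseline in lesion size at week 2 and 4", followed by "Difference in change from baseline in lesion size at week 2 and 4 between ILTAC-10, ILTAC-20, ILTAC-40". Section 2.0(c), Aim 1, gives the unit: "Lesion size will be measured in centimeters at baseline and during the week 2 and 4 visit". Section 7.0(a) gives the test: "Continuous variables, such as NRS pain scale, markers of inflammation, and lesion size, will be analyzed by T-test". No percent, ratio or log scale is named, so change in centimetres is the natural reading.

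No baseline covariate or stratification by size appears anywhere. Section 7.0(c) relies on design alone: "Confounding and effect modification will be addressed by randomization of the subjects and blinding of both the investigators and the participants".

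The volume table in 2.0(a) (Figure 1) covers lesions from under 0.5 cm to 5.0 cm, and the eligibility criteria set no minimum size. Up to three anatomic areas may be treated per patient. The plan does not say which lesion, or what sum or mean, enters the analysis.

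**The concern.** A lesion cannot shrink by more than its starting size. Complete resolution of a 0.8 cm nodule is a change of -0.8 cm. A 20% reduction of a 4.5 cm abscess is -0.9 cm (0.2 x 4.5). If response is even roughly proportional to size, part of the spread in centimetre change is simply spread in starting size. That part is known at Visit 1 and could be removed, but the t-test leaves it in the error term.

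What is at stake is precision in the ILTAC-saline and dose-versus-dose comparisons of lesion size at weeks 2 and 4. A real difference could be missed, or estimated with a wider interval than the data require.

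**Working it through.** **The plan's own figure.** Table 1 in 3.0(b) concerns pain, not lesion size. With SD 1 at both times and correlation 0.1, the SD of change is sqrt(1 + 1 - 2 x 0.1) = 1.342. With 30 per arm and a difference of 1, the noncentrality is 1 / (1.342 x sqrt(2/30)) = 2.89. The noncentral t with 58 df gives power 0.81021, exactly as printed. There is no corresponding figure for lesion size.

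**Inputs.** From the documents: 30 per arm, two-sided alpha 0.05, and a size table ending at 5.0 cm. Assumed, because the documents are silent: the distribution of baseline size B, the mean shrinkage fraction f in each arm, and its between-patient SD s (which is also the SD of the remaining fraction, 1 - shrinkage).

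**Proportional shrinkage, worked by hand.** Take B uniform on 0.5-5 cm.
- Mean of B = 2.75. Var(B) = 4.5²/12 = 1.6875. E(B²) = 2.75² + 1.6875 = 9.25.
- Variance of change in an arm = f² x Var(B) + s² x E(B²).
- With s = 0.25, the second term is 0.0625 x 9.25 = 0.578 in both arms.
- f = 0.4: 0.16 x 1.6875 + 0.578 = 0.848. f = 0.6: 0.36 x 1.6875 + 0.578 = 1.186. Average 1.017.
- Expected difference = 0.2 x 2.75 = 0.55 cm.
- t-test: SE = sqrt(2 x 1.017/30) = 0.260; 0.55/0.260 = 2.11; power about 55%.
- Adjusted for B with a common slope, each arm's slope is 0.1 from the average. Residual variance = 0.578 + 0.1² x 1.6875 = 0.595; SE = sqrt(2 x 0.595/30) = 0.199; 0.55/0.199 = 2.76; power about 77.5%.
- Share of the variance of change due to baseline size: (1.017 - 0.578)/1.017 = 43%.

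**Simulation.** 20,000 trials per row, 30 per arm. Follow-up size is truncated at zero, which explains small departures from the hand figures. The arms differ by 0.2 in mean remaining fraction, except in the last row.

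| Baseline (cm) | Remaining fraction | SD | t-test | ANCOVA | Points lost |
|---|---|---|---|---|---|
| 0.5-5 | 0.6 v 0.4 | 0.25 | 54% | 78% | 24 |
| 0.5-5 | 0.6 v 0.4 | 0.30 | 45% | 62% | 17 |
| 0.5-5 | 0.8 v 0.6 | 0.30 | 56% | 62% | 7 |
| 0.5-5 | 0.6 v 0.4 | 0.40 | 31% | 39% | 8 |
| 1-3 | 0.6 v 0.4 | 0.25 | 72% | 83% | 11 |
| 1-3 | 0.6 v 0.4 | 0.30 | 59% | 67% | 8 |
| 1-3 | 0.8 v 0.6 | 0.30 | 64% | 67% | 3 |
| 1-3 | 0.6 v 0.4 | 0.40 | 39% | 43% | 4 |
| 0.5-5 | 0.4 cm extra shrinkage at any size, residual SD 0.6 cm | - | 69% | 69% | 0 |

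Points lost are taken before rounding. With no treatment effect, both tests reject in about 5% of trials.

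**Percent change as an alternative.** In the last row, a t-test on percent change has 49% power against 69% for centimetre change. Under proportional shrinkage it does better than either (86% in the first row). Its merit therefore depends on a model that the documents cannot confirm.

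**The case against.** The strongest reply is that nothing here is invalid. Size is measured before treatment, allocation is random, and the volume rule is the same in every arm, saline included: "The volume of ILTAC or NS administered is calculated based on the largest dimension of the HS lesion". Size and volume are balanced in expectation, and the type I error holds. All of this stands.

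Three stronger readings are tempting, and the documents do not support them.
- *The test confuses treatment effect with lesion size.* It does not, for the reasons just given.
- *Scaling volume to size causes the loss.* Section 2.0(a) sets volume by size but says nothing about how response depends on size. That step would be the reader's inference, and scaled volume does not of itself reduce power.
- *Chance imbalance in starting size is a further harm.* With SD 1.30 cm, the SE of the baseline difference between two arms is 1.30 x sqrt(2/30) = 0.34 cm. At 40% shrinkage this moves the centimetre difference by 0.4 x 0.34, about 0.13 cm. That variation is the f² x Var(B) term already in the t-test's standard error, so it must not be counted twice.

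It is also fair to say that the 0.8 cm and 4.5 cm example does not by itself show a fault, since the t-test compares arm means and ranks no patients. Section 2.0 excludes sinus-tract networks and confluent nodules as treatment sites, so the 0.5-5 cm spread may be too wide. Finally, this is one of 16 listed secondary outcomes, and the sample size was set for pain.

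What remains is that a covariate already in hand goes unused. In these scenarios, using it costs nothing material when it does not help.

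**Conclusion.** The concern holds as a minor point about precision on a secondary endpoint. Under the assumed inputs, the power lost against ANCOVA runs from about 0 to about 24 points. The upper end needs proportional shrinkage, a wide spread of baseline size and a fairly uniform response between patients. A narrower size range, a more variable response or shrinkage unrelated to size reduces the loss, in the last case to nothing. These are illustrations, not estimates or bounds, because the documents give no lesion-size SD, effect or distribution. It cannot be said that the planned test will lose power, only that it can. The trial's validity and its primary pain outcome are not affected by this point.

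**What to change.** In 7.0(a), remove lesion size from the t-test sentence. Analyse lesion size at week 2 and at week 4 with a linear model containing treatment arm and baseline lesion size. State the following with it:
- one value per patient, defined the same way at baseline and follow-up, for example the sum of the diameters of the injected lesions;
- a resolved lesion is scored as 0 cm;
- percent change and the number of patients with complete resolution are reported descriptively only, because a percent-change t-test can do worse than the planned analysis.

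No patients, visits or measurements are added. The per-patient value must be settled before the model can be written, but the planned t-test needs that rule too. The downside is small: the model assumes a roughly linear relation to baseline size and uses one degree of freedom.

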#### *Aim 2*

- To investigate the side effect profile of ILTAC-10, ILTAC-20, and ILTAC-40 in the treatment of acute HS flares.

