Participant eligibility will be assessed according to inclusion and exclusion criteria in 2.0a. A member of the study team will describe the study and answer any of the participant's questions. The participant will then be consented and enrolled. The initial visit and all subsequent visits will include documentation of NRS pain scale (Appendix B), HS-PGA, Hurley Stage (Appendix C), clinical markers of inflammation, and lesion size (as specified in our standard approach to care. Photographs of the lesions will be obtained. The study personnel will administer a patient satisfaction survey and the PROMIS questionnaire, which will take 15 minutes to complete (Appendix D and Appendix F [or Appendix G if pediatric]). Chart review will record demographic information (age, gender, race, ethnicity, smoking status, and BMI) and complete blood count (CBC), basic metabolic profile (BMP), liver function tests (LFT), erythrocyte sedimentation rate (ESR), c-reactive protein (CRP), and interleukin-6 (IL-6). The lab work is a standard of care at the HSC independent of research objectives. The patient will receive an injection, not to exceed 2 mL per anatomic area, in up to 3 anatomic areas (total of 3mL). The patient will be counseled regarding potential side-effects of the treatment (Appendix H) and asked to monitor accordingly. No other changes to the patient's HS medication regimen will be made for the duration of the study.

- Phone Contact 1 (2-day post-treatment)

Since triamcinolone has a half-life of 18 to 36 hours, the initial patient follow-up will be a phone call at 2 days post-injection, lasting 15 minutes. Study personnel will administer a patient satisfaction survey and the PROMIS questionnaire (Appendix D, and Appendix F [or Appendix G if pediatric]). Additionally, patients will be asked if they experienced any side effects, including thinning/atrophy of skin, acneiform lesions, capillary dilation, and/or dyschromia.

- Phone Contact 2 (6 days post-injection)

This 15 minute phone call will be 6 days post-injection and will involve administering the patient satisfaction survey, the PROMIS questionnaire, and questions about side effects.

- Visit 2 (2 weeks post-injection)

- The initial screening visit examination will be repeated at week 2. Additionally, the patient will be asked to identify side effects. A patient

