satisfaction survey as well as the PROMIS questionnaire will also be administered, again lasting 15 minutes. Blood count (CBC), basic metabolic profile (BMP), liver function tests (LFT), erythrocyte sedimentation rate (ESR), c-reactive protein (CRP), and interleukin-6 (IL-6) will be routinely obtained at the two week visit. Serum 8 AM cortisol and ACTH will also be routinely obtained at the two week visit. The two week visit and lab draw are the standard of care for HS patients independent of research objectives.

- Visit 3 (Final visit - 4 weeks post-injection)
  - The initial screening visit examination will be repeated at week 4. Additionally, the patient will be asked to identify side effects. A patient satisfaction survey as well as the PROMIS questionnaire will also be administered, again lasting 15 minutes. Blood count (CBC), basic metabolic profile (BMP), liver function tests (LFT), erythrocyte sedimentation rate (ESR), c-reactive protein (CRP), and interleukin-6 (IL-6) will be routinely obtained at the four week visit. Serum 8 AM cortisol and ACTH will also be routinely obtained at the four week visit. The four week visit and lab draw are the standard of care for HS patients independent of research objectives.

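### No side-effect outcome counts the patients in each arm who had at least one side effect over the 4 weeks, and the four contact-specific proportions do not determine that number

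*Combined protocol and SAP*

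**What the plan says.** Aim 2 is "To investigate the side effect profile of ILTAC-10, ILTAC-20, and ILTAC-40 in the treatment of acute HS flares". Treatment is given once, at enrollment, and the Study Calendar (Section 5.0f) places side-effect assessments at day 2, day 6, week 2 and week 4.

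Secondary Outcomes lists two side-effect items: "Proportion of subjects reporting side effects at days 2, 6, 14, and 28" and "Difference in proportion of subjects reporting side effects at days 2, 6, 14, and 28 between ILTAC-10, ILTAC-20, ILTAC-40". Section 7.0a gives the analysis: "Categorical variables, including presence of side effects, drainage, and physical function, will be analyzed with chi square tests". Cortisol and ACTH are separate outcomes. Neither Section 2.0c (measures for each aim) nor Section 7.0 defines a per-patient summary across contacts.

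The questions are described in Section 2.0b, Schedule of Study Visits. At the initial visit, "The patient will be counseled regarding potential side-effects of the treatment (Appendix H) and asked to monitor accordingly". At day 2, "patients will be asked if they experienced any side effects, including thinning/atrophy of skin, acneiform lesions, capillary dilation, and/or dyschromia". The day-6 call involves "administering the patient satisfaction survey, the PROMIS questionnaire, and questions about side effects". For the week-2 and week-4 visits the text is "Additionally, the patient will be asked to identify side effects". After day 2 the period that each question covers is not stated.

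The Hypothesis section expects no difference in side-effect profile between the triamcinolone arms and saline.

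**The concern.** After a single injection, the first safety question is how many patients in each arm had a side effect. The listed outcomes answer a different one: how many reported a side effect at each contact. A patient affected only at day 6 and another affected only at day 14 fall in different tables, and no table counts both.

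Two arms could therefore show the same four proportions and differ widely in the number of patients affected. The hypothesis also compares triamcinolone with saline, whereas the listed difference outcome names only the three doses. With about 30 patients per arm, chosen for pain, a run of non-significant contact-level tests could be read as support for the no-difference hypothesis without a per-patient risk ever being shown.

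**Working it through.** **The plan's own figure.** The documents give no rate, sample size or power for side effects. The only sample-size calculation is for pain (Section 3.0b, Table 1). With correlation 0.1, the SD of the change is √(1 + 1 − 2 × 0.1) = 1.342. With 30 per arm and a difference of 1, the noncentrality is 1 / (1.342 × √(2/30)) = 2.89 on 58 degrees of freedom. Two-sided power at 0.05 is then 0.810, against 0.81021 in the table. The figure reproduces. It matters here only as the source of 30 per arm.

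**What the four proportions determine.** Let p be the proportion reporting at each of the four contacts (assumed equal, for illustration). The proportion reporting at any contact is smallest, at p, if the same patients report every time. It is largest, at 4p (capped at 1), if different patients report each time. If contacts are independent it is 1 − (1 − p)⁴.

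| p at each contact (assumed) | Same patients | Independent | Different patients |
|---|---|---|---|
| 5% | 5% | 18.5% | 20% |
| 10% | 10% | 34.4% | 40% |
| 20% | 20% | 59.0% | 80% |

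In an arm of 30, 10% is 3 patients per contact. Over the 4 weeks that could be 3 patients or 12.

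**Possible effect on power (illustration only).** Assume a 3% chance of a new effect per contact in one arm and 12% in another, 30 per arm, and an uncorrected chi-square test evaluated by exact binomial enumeration.

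- Any effect by day 28: 1 − 0.97⁴ = 11.5% against 1 − 0.88⁴ = 40.0%. Power is 74%.
- One contact, effects not persisting but able to recur: 3% against 12%. Power is about 25%.
- All effects persisting: day 28 alone shows 11.5% against 40.0%. Power is 74%, the same as the any-time measure.

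**A case that goes the other way.** Assume 10% background reports per contact in both arms and a 25-point excess in one arm at day 28 only.

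- Day 28 alone: 10% against 35%. Power is 66%.
- Any time: 1 − 0.9⁴ = 34.4% against 1 − 0.9³ × 0.65 = 52.6%. Power is 30%.

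With 5% background the same calculation gives 78% at day 28 and 45% for any time. Pooling helps when the excess is spread over contacts and hurts when it is confined to one late contact.

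**The case against.** **Time-specific proportions also describe a profile.** They show onset and resolution, and a pooled measure can dilute a late effect, as calculated above. This stands: the time-point comparisons should not be demoted.

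**The missing summary can be derived later from the same records.** True, and it limits the severity. But an unplanned summary is chosen after the data are seen, and planning it costs almost nothing.

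**The day-28 question might cover the whole period since injection, making that proportion cumulative already.** The text does not say so. The possibility is a further reason to state the recall window.

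Three stronger readings are tempting, and the documents do not support them.

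- *Transient effects are mostly missed.* The day-2 call asks what patients have experienced, patients are told to self-monitor, and Safety Outcomes describes adverse-event monitoring throughout the study. If each contact covers the time since the last, days 0 to 28 are covered without a gap. If contacts recorded only same-day presence and onset were uniform over 28 days, a 1-day effect would be caught 4/28 = 14% of the time, a 7-day effect (2 + 4 + 7 + 7)/28 = 71%, and a 14-day effect always. The documents give neither durations nor the recall window. Pooling the same four reports would not recover a missed event in any case.
- *Twelve dose-pair tests would fall to three.* The plan does not specify pairwise testing. One three-arm table per contact would give four tests against one.
- *The any-time measure is never worse, or the current plan hides real differences.* The late-effect case refutes the first. On the second, in the no-persistence illustration the chance of at least one significant result in four independent tests is 1 − (1 − 0.255)⁴ = 69%. The cost of four unadjusted tests is instead a false-positive chance of up to 1 − 0.95⁴ = 18.5% if they are independent.

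**Conclusion.** The point holds as a gap in the outcome definition. Side effects are specified only contact by contact, no outcome gives the proportion of patients per arm with at least one side effect over the 4 weeks, and the four proportions as listed do not determine it. At an assumed 10% per contact, the per-patient figure can lie anywhere from 10% to 40%. The width of that range depends on the assumed rate. The indeterminacy does not, unless a contact's question is taken to cover the whole period since injection, which the text does not state.

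The power gain (74% against about 25% at one contact) rests on assumed rates, a constant excess at every contact and no persistence. It disappears at day 28 if all effects persist, and reverses for an effect confined to day 28. It is not a general reason to replace the existing outcomes. This is a cheap improvement to a secondary safety outcome and leaves the primary analysis untouched.

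**What to change.** In Secondary Outcomes and Section 7.0a, add one summary outcome for Aim 2: the proportion of patients with at least one side effect reported at any contact through day 28, overall and by type. Report it for all four arms with risk differences and 95% confidence intervals. Include each dose against saline, since that is the comparison in the Hypothesis section, as well as the comparisons between doses.

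Keep the proportions at days 2, 6, 14 and 28 alongside it. In Section 2.0b, word the question at every contact as covering the time since the last contact (since injection, at day 2).

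The cost is one more summary, a sentence of question wording, and a rule for missed contacts: for example, count reports from the contacts made and show the number of contacts made in each arm. No extra visit or assessment is needed.
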